9.2.1. Inclusion criteria

The HCPs must meet the following criteria to be eligible for inclusion in the survey:

- HCPs are aware of the insulin product Humalog 200 units/ml KwikPen; and
- HCPs are involved in the treatment and management of patients with diabetes.

Patients must meet all of the following criteria to be eligible for inclusion in the survey:

- Patients are 18 years or older;
- Patients have diabetes; and
- Patients have been prescribed Humalog 200 units/ml KwikPen.

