The additional risk minimisation measures will include a Direct Healthcare Professional Communication (DHPC) that will be distributed to all healthcare professionals (HCPs) who are expected to be involved in the treatment and management of patients with diabetes; physicians, nurses, and where applicable, pharmacists who are expected to dispense medications for diabetes management. A patient communication document will be distributed to prescribing HCPs targeted for the DHPC. The DHPC will ask HCPs to provide the patient communication to patients receiving their initial prescription of Humalog 200 units/ml KwikPen. Where approved,

a web address link to the patient communication may be provided in the DHPC to allow either printing of the communication during the patient visit or provision of the link to the patient to enable the patient to directly access the communication.

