9.4. Data sources

In this survey, data sources for HCPs may be Lilly's lists of HCPs who received the DHPC (in countries where local privacy regulations or standard practices allow this list to be provided to UBC) and/or UBC's HCP reference files or panels. From these data sources, random samples of HCPs will be invited to participate in the survey and to invite patients to participate in the survey.

Structured, self-administered surveys (Appendix I.1 and Appendix I.3) comprised of closed-ended questions or statements with multiple response choices (that is, questions or statements asking the respondents to choose from a defined list of responses) will be used to collect the survey data. The surveys will collect data on respondent characteristics and their responses to

the risk understanding questions. The data collected from the surveys will be used to inform the evaluation of the effectiveness of the risk minimisation measures.

The survey is designed to be completely voluntary and anonymous to prevent the collection of any personal identifying information from participants. Each participant will be given a unique code to access the survey. Each code is deactivated upon its use to prevent the code from being used to complete the survey twice. Each code is randomly assigned and not tracked; therefore, no identification of patients who have or have not responded can be performed. The participants do not have to actively ‘decline to complete the survey’. Therefore, there is no ability to track which participants are actively deciding to not complete the survey. This survey design encourages patient participation and answer honesty by ensuring that the responses are completely anonymous.

Each survey will begin with a screening module with questions to confirm eligibility. Depending on the answers to the screening questions, survey participation will either be terminated or continued. If ineligible, the respondent is immediately notified with a “thank you” message that survey participation has ended. If eligible, the respondent is allowed to continue survey participation.

HCPs:

Screening questions:

- Agreement to participate
- Involved in the management of patients with diabetes
- Prior or current employment by Lilly, UBC, or any national medical governing body, such as but not limited to EMA, MHRA, and BfArM
- Awareness of Humalog 200 units/ml KwikPen

Data on demographic characteristics:

- Age
- Sex
- Role at facility
- Facility type
- Country

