- HCP medical specialty (for example, endocrinology, primary care)
- Number of years practicing medicine/nursing
- Number of Humalog 200 units/ml KwikPen-treated patients the HCP managed in the 12 month period preceding the survey (self-reported)

Data pertaining to evaluation of the effectiveness of the risk minimisation measures:

The survey includes questions/statements that will assess the risk understanding and behaviour of the HCPs. The understanding level and behaviours will be analysed using descriptive statistics and CIs and will be used to determine the effectiveness of the risk minimisation measures:

- Awareness of the DHPC on the correct use of Humalog 200 units/ml KwikPen
- Understanding of the key risk messages

- Self-reported practices with respect to communication of the key risk messages in clinical practice

Patients:

Screening questions:

- Agreement to participate
- Diagnosis of diabetes
- Prescribed Humalog 200 units/ml KwikPen
- 18 years or older
- Prior or current employment by Lilly, UBC, or any national medical governing body, such as but not limited to EMA, MHRA, and BfArM

Data on demographic characteristics:

- Age
- Sex
- Country
- Education status
- Length of time with diabetes
- Length of time on any insulin therapy
- Length of time on Humalog 200 units/ml KwikPen
- Length of time on Insulin used prior to Humalog 200 units/ml

Data pertaining to evaluation of the effectiveness of the risk minimisation measures:

The survey includes questions/statements that will assess the risk understanding and behaviour of patients. The understanding level and behaviours will be analysed using descriptive statistics and CIs and will be used to determine the effectiveness of the risk minimisation measures:

- Awareness of the Important Safety Information for Humalog 200 units/ml KwikPen
- Receipt of or access to the Important Safety Information
- Understanding of the key risk messages
- Patient behaviour with respect to the key risk messages

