9.7. Data analysis

Data collected from the survey will be reported as descriptive statistics. Frequency distributions with 95% CIs will be calculated for respondent responses to all questions that address the survey objectives. Responses to each question relating to the key risk messages will be categorised as “Correct response” and “Incorrect response”. “I don’t know” is generally categorised as an incorrect response unless otherwise specified.

In addition to the overall analysis, survey data will be analysed to determine if there are any differences by country and, for HCPs, medical speciality. Sub-group analyses will include all requested subgroups including patients switched from other 100 units/ml insulins, Humalog 100 U/ml, how long patients were on insulin, and which other insulins have been used as captured in the questionnaire. Additionally, a subgroup analysis will be performed to identify possible differences in the responses based on length of Humalog 200 units/ml use.

The following will be reported as part of the analysis:

HCPs:

- *Survey administration*
 - The number of survey invitations issued by strata (i.e., by country and specialty)
 - The number of survey invitations returned due to incorrect mailing address of HCPs invited to participate in the survey
 - The number of HCPs who responded to the invitation to participate in the survey
 - The number of HCPs eligible for participation in the survey
 - The number of ineligible HCPs along with the reasons for ineligibility
 - The number of eligible HCPs who completed the survey
- *Demographic characteristics of participants*
 - Distribution of participants by age groups
 - Distribution of participants by sex
 - Distribution of participants by practice setting
 - Distribution of participants by country
 - Distribution of participants by medical specialty
 - Distribution of participants by years in medical practice
 - Distribution of participants by number of patients treated with Humalog 200 units/ml KwikPen
- *Responses to questions pertaining to the survey objectives:*
 - Awareness of the DHPC on the correct use of Humalog (insulin lispro) 200 units/ml KwikPen
 - Understanding of the risk messages
 - Self-reported practices with respect to communication of the key risk messages in clinical practice

Patients:

- *Survey administration*
 - The number of HCPs asked to invite patients to participate
 - The number of invitations provided to HCPs

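### DHPC awareness is measured only among HCPs who already know the product, so it overstates the communication's reach, and the permitted mix of sampling frames can confound country comparisons of it

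*Protocol*

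**What the plan says.** **Audience.** Protocol 4.1 says the DHPC is to be "distributed to all healthcare professionals (HCPs) who are expected to be involved in the treatment and management of patients with diabetes". Section 7 describes a similarly wide audience. Neither limits it to HCPs who know the product.

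**Eligibility.** Section 9.2.1 requires that "HCPs are aware of the insulin product Humalog 200 units/ml KwikPen; and". Section 4.4 says the same, and 9.4 enforces it with a screening item, "Awareness of Humalog 200 units/ml KwikPen". Ineligible respondents are thanked and the survey ends.

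**Use of the result.** Section 9.4 lists "Awareness of the DHPC on the correct use of Humalog 200 units/ml KwikPen" among the HCP items analysed with confidence intervals to determine effectiveness, and 9.7 reports it. Section 9.9 explains the reading: a respondent who reports not having received the communication is taken as a sign that dissemination was less than optimal.

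**Frame.** Section 9.4 says the HCP source may be the sponsor's "lists of HCPs who received the DHPC (in countries where local privacy regulations or standard practices allow this list to be provided to UBC"), and/or the vendor's "HCP reference files or panels. From these data sources, random samples of HCPs will be invited".

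**Comparison and pooling.** Section 9.6 reports results by country and combined. Section 9.7 looks for differences by country and specialty. Invitations are counted by country and specialty, not by frame. Section 9.7 also reports "The number of ineligible HCPs along with the reasons for ineligibility".

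**The concern.** Two separate mechanisms affect the same result.

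First, the screen acts on a variable close to the outcome. DHPC awareness is read as a measure of dissemination, and the HCPs most likely to be dissemination failures are those who have not heard of the product. They are removed before the question is put, so they cannot give the answer that 9.9 would count against the programme.

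Second, the two permitted frames measure different things. On a recipient list, receipt (or at least mailing) is fixed by construction, so the result is recall given receipt. On a vendor panel it is receipt and recall combined. Because access to the list depends on local privacy rules, frame would tend to follow country. A difference that is purely one of frame would then look like a country difference, and the pooled value would depend on how many respondents came from each source. The country weighting planned in 9.5 cannot remove an effect that is tied to country.

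At stake is what the final report can say about how far the DHPC reached its intended audience. Section 9.2 says selection bias will be largely prevented and expects no geographic variability. Section 9.9 discusses self-selection, recall and self-report, but neither the screen nor the frames.

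**Working it through.** **1. The plan's own figures.** Equation 1 in 9.5 is p ± 1.96·√(p(1−p)/n). With n = 280 the half-widths at p = 50, 60, 70, 80 and 90% are 5.9, 5.7, 5.4, 4.7 and 3.5 points, exactly as in Table 1. The point does not depend on Table 1, which serves here as a yardstick.

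**2. The screen.** Let D = aware of the DHPC and A = aware of the product. Assume D implies A, because the DHPC names the product. Then

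P(D | A) = P(D) / P(A) ≥ P(D).

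The protocol gives neither probability. Taking P(D) = 40% for illustration:

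| P(A), assumed | Factor 1/P(A) | Reported P(D given A) | 95% CI, n = 280 | Contains 40%? |
|---|---|---|---|---|
| 90% | 1.11 | 44.4% | 38.6 to 50.3 | yes |
| 80% | 1.25 | 50.0% | 44.1 to 55.9 | no |
| 70% | 1.43 | 57.1% | 51.3 to 62.9 | no |
| 60% | 1.67 | 66.7% | 61.1 to 72.2 | no |
| 50% | 2.00 | 80.0% | 75.3 to 84.7 | no |

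The other way round: if the reported value is q and a share u of otherwise eligible HCPs is product-unaware, the overstatement is q − q(1−u) = q·u. It exceeds the half-width h once u > h/q:

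- q = 50%: 5.9/50, about 12%
- q = 65%: h = 1.96·√(0.65·0.35/280) = 5.6 points; 5.6/65, about 9%
- q = 80%: 4.7/80, about 6%

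A fairly small unaware share is therefore enough to put the bias beyond the stated precision.

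**3. The frame.** Let c = recall given receipt, r = share of a panel that received the DHPC, and b = product awareness among HCPs not aware of the DHPC. Before the screen, awareness is x = c on the list and x = c·r on a panel. After the screen it is x / (x + (1−x)·b). All three inputs are assumed. With c = 60% and b = 50%, the list gives 0.60/(0.60 + 0.40·0.50) = 75.0%. Panels give:

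| r | Panel before screen | Panel after screen | Gap to list after screen |
|---|---|---|---|
| 90% | 54% | 70.1% | 4.9 points |
| 70% | 42% | 59.2% | 15.8 points |
| 50% | 30% | 46.2% | 28.8 points |

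Recall is the same in both frames throughout. Over c = 50 to 70%, r = 50 to 90% and b = 30 to 70%, the gap runs from 3.6 to 33.4 points. For scale, if 280 split evenly into about 93 per country (also an assumption), the half-width for a difference between two countries near 50% is 1.96·√(2·0.25/93) = 14.4 points.

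Pooling the r = 70% case: with 30% of respondents from the list, 0.30·75.0 + 0.70·59.15 = 63.9%; with 75% from the list, 0.75·75.0 + 0.25·59.15 = 71.0%. The same recall gives two pooled answers.

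**The case against.** The strongest case on the other side has five parts.

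- **The screen is a sensible target population.** An HCP who has never heard of the product cannot usefully be tested on its messages. This stands for the understanding questions. A reader might infer that the understanding results are biased upward too. The documents do not show it: the argument above concerns DHPC awareness only.
- **DHPC awareness is not a listed endpoint.** The bullets in 4.5 and 9.1 are understanding, provision of the patient communication, and discussion. The majority criterion there concerns awareness of the key risks. A reader might infer that the screen could carry the study across that criterion. It does not apply to DHPC awareness, so this inference fails. Section 9.4 nevertheless uses the item to determine effectiveness.
- **Screen-outs are already reported with reasons.** A reader could partly rebuild the wider denominator. That stands and is why the fix is cheap, but the protocol does not commit to the calculation, and the counts do nothing about frame.
- **Mixed frames are allowed, not planned.** The wording is permissive and the third country is undecided. The DHPC is also meant for all diabetes-treating HCPs, so a panel may overlap heavily with the list. At r = 90% the gap is only about 5 points. This stands: the frame problem is conditional and its size unknown.
- **Country tables may already separate frames.** If each country used a single frame, they would. Country and frame would then be fully confounded, which is the difficulty rather than its solution.

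It would also go too far to say that the DHPC is what creates product awareness. The survey runs 12 to 18 months after launch, other sources are likely, and the argument does not need that claim.

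**Conclusion.** The concern holds for DHPC awareness as a measure of reach. As planned, 9.7 will report awareness among product-aware HCPs, which overstates awareness among all otherwise eligible HCPs by 1/P(product-aware): 1.11 at 90% and 1.43 at 70%. The direction follows from the design, given that an HCP aware of the DHPC knows the product it names. The size cannot be derived from the protocol.

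The frame point is conditional. Section 9.4 permits different frames by country and nothing harmonises them. If they differ, country differences in DHPC awareness are confounded with frame and the pooled value depends on the mix. The illustrative gaps of about 4 to 33 points rest wholly on assumed inputs.

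The documents do not support extending this to the understanding results or to the majority criterion. Nor do they call for abandoning the country comparison that 9.7 plans.

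**What to change.** - **In 9.7, report DHPC awareness on two denominators:** (a) product-aware respondents, labelled as such; and (b) all HCPs who pass the other screening questions, with product-unaware HCPs counted as not aware. The screening counts in 9.7 supply what is needed. Product awareness comes last among the HCP screening items in 9.4. If the survey keeps that order, everyone who fails there has passed the rest; this should be confirmed in the programmed survey.
- **Record the frame** (recipient list, or vendor file or panel) by invitation batch. This identifies no one, so it is compatible with the untracked access codes described in 9.4.
- **Tabulate DHPC awareness by frame**, and interpret any country difference with the frame shown beside it.
- **Name both limits in 9.9.** Denominator (b) corrects for the screen only, not for the self-selection already acknowledged there.
- **Keep the eligibility criterion** for the understanding questions.

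The cost is one extra table, one frame variable and a sentence or two of text. The likely downside is a less favourable reach figure. The frame variable should be set up before invitations go out, because it may not be recoverable afterwards.

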9.2.2. Exclusion criteria

The HCPs meeting any of the following criteria will not be included in the survey:

- Employed in full time research or hospital administration (i.e., non-practising physicians)
- Current or past employment by Lilly, UBC, or any national regulatory agency, such as but not limited to EMA, Medicines and MHRA and BfArM

Patients meeting any of the following criteria will not be included in the survey:

- Patients with diabetes who are not prescribed Humalog 200 units/ml KwikPen
- Current or past employment by Lilly, UBC, or any national regulatory agency, such as but not limited to EMA, MHRA, and BfArM

9.3. Variables

The surveys will collect participants' understanding of the key safety messages in the risk minimisation communication and information about potential behaviour. Additionally, the HCP survey will collect information on demographic characteristics that include age, sex, geographical location, HCP specialty, and practice information. The HCP-identifying information will be collected for the purposes of providing HCP honorarium as allowed by local laws and country regulations. The patient survey will collect a variety of respondent demographic characteristics that include age, sex, geographical location, and their length of experience with any insulin therapy and Humalog 200 units/ml KwikPen. Patient-identifying information will be collected for the purposes of providing payment for participation where applicable.

9.4. Data sources

In this survey, data sources for HCPs may be Lilly's lists of HCPs who received the DHPC (in countries where local privacy regulations or standard practices allow this list to be provided to UBC) and/or UBC's HCP reference files or panels. From these data sources, random samples of HCPs will be invited to participate in the survey and to invite patients to participate in the survey.

Structured, self-administered surveys (Appendix I.1 and Appendix I.3) comprised of closed-ended questions or statements with multiple response choices (that is, questions or statements asking the respondents to choose from a defined list of responses) will be used to collect the survey data. The surveys will collect data on respondent characteristics and their responses to

the risk understanding questions. The data collected from the surveys will be used to inform the evaluation of the effectiveness of the risk minimisation measures.

The survey is designed to be completely voluntary and anonymous to prevent the collection of any personal identifying information from participants. Each participant will be given a unique code to access the survey. Each code is deactivated upon its use to prevent the code from being used to complete the survey twice. Each code is randomly assigned and not tracked; therefore, no identification of patients who have or have not responded can be performed. The participants do not have to actively ‘decline to complete the survey’. Therefore, there is no ability to track which participants are actively deciding to not complete the survey. This survey design encourages patient participation and answer honesty by ensuring that the responses are completely anonymous.

Each survey will begin with a screening module with questions to confirm eligibility. Depending on the answers to the screening questions, survey participation will either be terminated or continued. If ineligible, the respondent is immediately notified with a “thank you” message that survey participation has ended. If eligible, the respondent is allowed to continue survey participation.

HCPs:

Screening questions:

- Agreement to participate
- Involved in the management of patients with diabetes
- Prior or current employment by Lilly, UBC, or any national medical governing body, such as but not limited to EMA, MHRA, and BfArM
- Awareness of Humalog 200 units/ml KwikPen

Data on demographic characteristics:

- Age
- Sex
- Role at facility
- Facility type
- Country
- HCP medical specialty (for example, endocrinology, primary care)
- Number of years practicing medicine/nursing
- Number of Humalog 200 units/ml KwikPen-treated patients the HCP managed in the 12 month period preceding the survey (self-reported)

Data pertaining to evaluation of the effectiveness of the risk minimisation measures:

The survey includes questions/statements that will assess the risk understanding and behaviour of the HCPs. The understanding level and behaviours will be analysed using descriptive statistics and CIs and will be used to determine the effectiveness of the risk minimisation measures:

- Awareness of the DHPC on the correct use of Humalog 200 units/ml KwikPen
- Understanding of the key risk messages

- Self-reported practices with respect to communication of the key risk messages in clinical practice

Patients:

Screening questions:

- Agreement to participate
- Diagnosis of diabetes
- Prescribed Humalog 200 units/ml KwikPen
- 18 years or older
- Prior or current employment by Lilly, UBC, or any national medical governing body, such as but not limited to EMA, MHRA, and BfArM

Data on demographic characteristics:

- Age
- Sex
- Country
- Education status
- Length of time with diabetes
- Length of time on any insulin therapy
- Length of time on Humalog 200 units/ml KwikPen
- Length of time on Insulin used prior to Humalog 200 units/ml

Data pertaining to evaluation of the effectiveness of the risk minimisation measures:

The survey includes questions/statements that will assess the risk understanding and behaviour of patients. The understanding level and behaviours will be analysed using descriptive statistics and CIs and will be used to determine the effectiveness of the risk minimisation measures:

- Awareness of the Important Safety Information for Humalog 200 units/ml KwikPen
- Receipt of or access to the Important Safety Information
- Understanding of the key risk messages
- Patient behaviour with respect to the key risk messages

